### 4.2.2 Safety in Hemodialysis Patients

A review of the aggregate safety data shows that CR845 was generally well tolerated in hemodialysis patients when administered after each dialysis session for up to 8 weeks at IV doses ranging from 0.5 mcg/kg to 6 mcg/kg. Although patients exposed to CR845 reported more adverse events compared with placebo patients, most events were mild or moderate in nature. Generally mild, transient paresthesias (facial tingling) and/or hypoesthesias (in different anatomic locations), mostly on the first week of dosing, as well as headache, dizziness, and somnolence, were the most frequently reported adverse events associated with CR845 administration. Of note, side effects (eg, dysphoria and hallucinations) commonly associated with centrally-acting kappa opioids were not reported in patients exposed to CR845. Consistent with its lack of affinity for mu-opioid receptors, CR845 did not cause euphoria or respiratory depression.

CR845-CLIN2101 evaluated the safety, pharmacokinetics, and efficacy of repeated IV doses of CR845 compared to placebo over an 8-week treatment period in 174 hemodialysis patients. As expected with patients on hemodialysis, a significant number of the reported serious adverse events (SAEs) were considered not treatment-related, but related to the disease and/or comorbid conditions. There were 31 (17.8%) of

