  9. Has at least 2 single-pool Kt/V measurements  $\geq 1.2$ , or at least 2 urea reduction ratio measurements  $\geq 65\%$ , or 1 single-pool Kt/V measurement  $\geq 1.2$  and 1 urea reduction ratio measurement  $\geq 65\%$  on different dialysis days during the 3 months period prior to screening;
  10. Prior to randomization:
    - a. Has completed at least four out of eight Worst Itching Intensity Numeral Rating Scale (NRS) worksheets from the start of the 7-day Run-in Period up to and including the pre-randomization assessment on Day 1;
    - b. Has a mean baseline Worst Itching Intensity NRS score  $\geq 5$ , defined as the average of all non-missing scores reported from the start of the 7-day Run-in Period up to and including the pre-randomization assessment on Day 1.

**To be eligible for inclusion into the Open-label Extension Phase of the study, each patient will have to fulfill the additional following criteria at the time of entry into the Open-label Extension Phase:**

11. Has received at least 30 doses of the planned 36 doses of study drug during the Double-blind Phase of this study;
12. Has a prescription dry body weight  $\geq 40$  kg;
13. Continues to meet inclusion criteria 1 through 7.

---

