## **8.7 Efficacy Analysis**

### **8.7.1 Primary Efficacy Endpoint**

The primary efficacy endpoint is defined as the proportion of patients achieving  $\geq 3$ -point improvement from baseline with respect to the weekly mean of the daily 24-hour Worst Itching Intensity NRS at Week 12 (Days 79 to 85) of the Double-blind Treatment Period.

The weekly mean of the 24-hour Worst Itching Intensity NRS score will be defined as the sum of the daily Worst Itching Intensity NRS scores reported during a specific week during the Double-blind Treatment Period (eg, Days 2 to 8, Days 9 to 15, Days 16 to 22, ... Days 79 to 85) divided by the number of days with nonmissing scores for that week. If the daily worst itching score is missing for  $>3$  days during a specific week, the corresponding weekly mean worst itching score will be set to missing. The baseline score will be defined as the average of the daily 24-hour Worst Itching Intensity NRS scores collected over the Run-in Period, including pre-randomization assessments collected on Day 1.

In the primary efficacy analysis, missing NRS data will be imputed using a multiple imputation (MI) approach, assuming that patients who discontinue double-blind treatment early would have similar Worst Itching Intensity NRS scores as other patients in their respective treatment arm that have complete data:

- Intermittent missing NRS scores will first be imputed using the Markov Chain Monte Carlo (MCMC) method implemented with the SAS MI procedure, which is appropriate for non-monotonic missing data.
- NRS scores missing after patients discontinue study drug early will then be multiply imputed with the SAS MI procedure using a method appropriate for

monotone missingness (eg, regression statement). Details on the MI procedure can be found in [Appendix 14.6](#).

- The proportion of patients who have an improvement from baseline with respect to the weekly mean of the daily 24-hour Worst Itching Intensity NRS score  $\geq 3$  points will be calculated for each imputed dataset. Differences between CR845 0.5 mcg/kg and placebo with respect to the primary endpoint will be compared using a logistic regression model containing terms for treatment group, baseline NRS score, use of prior anti-itch medication, presence of specific medical conditions, and country/region.
- Results of the logistic regression on the multiply imputed data sets will be summarized by the SAS MIANALYZE procedure.

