The final p-value will be calculated using the Cui, Hung, Wang (CHW) procedure where the z-score is a weighted average of the z-score at the interim and the z-score observed for data collected after the interim, following the formula below.

$$Z_{\text{final}} = Z_{\text{interim}} * \sqrt{(n/N)} + Z_{\text{post-interim}} * \sqrt{(1 - n/N)}$$

where n is the number of patients at the interim and N is the initial number of patients planned (300).

Sensitivity analyses of the primary efficacy endpoint will be conducted to evaluate the robustness of study results under different assumptions and imputation algorithms. For each of these sensitivity analyses, the final p-value will be calculated based on the CHW procedure, using the formula specified above.

- **Sensitivity 1:** Early discontinuations as nonresponders

Patients who discontinue study drug early will be considered nonresponders. The imputed data will be analyzed using a logistic regression model similar to the primary analysis.

- **Sensitivity 2:** Multiple imputation; missing not at random (MNAR)

This sensitivity analysis is an implementation of a pattern mixture model that draws from different populations based on the reason for withdrawal.

- Intermittent missing NRS scores will first be imputed using the MCMC method with the SAS MI procedure, which is appropriate for non-monotonic missing data.
- For patients who discontinued study drug due to adverse events, NRS scores missing after discontinuation will be imputed using the distribution of the baseline value of all patients' daily worst itching score assuming a trimmed normal (from 5 to 10).
- For patients who discontinue due to reasons other than adverse event, missing NRS scores after patients discontinue study drug early will be multiply

imputed using multiple calls of the SAS MI procedure using data from patients within the same treatment group that have complete data at that time. The proportion of patients who have an improvement from baseline with respect to the weekly mean of the daily 24-hour Worst Itching Intensity NRS score  $\geq 3$  points will be calculated for each imputed dataset

- Similar to the primary analysis, results of the logistic regression on the multiply imputed data sets will be summarized by the SAS MIANALYZE procedure.
- **Sensitivity 3:** Tipping point analysis  

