## 14.6 Statistical Appendix

This appendix provides further details related to the treatment of missing data for the primary and sensitivity analyses of the primary endpoint.

For multiple imputations and other instances where random seeds are required, the values used (in order) are:

8392857  
2985729  
1843255  
9086284  
5547484  
8017456  
9597295  
2252256  
4821871  
9852467  
5126715  
3232132  
9841654  
3645284  
1587345

Note that not all seeds may be required in programming the multiple imputations. If additional seeds are needed, they will be chosen by adding 1 to each of the values above, again using them in order.

The number of imputations for the multiple imputations will be 20.

For the primary analysis, a multi-stage process will be applied:

Stage 1: Subjects will have their 11-point NRS scores imputed. First, using all visits, intermittent missing data will be imputed using the Markov Chain Monte Carlo (MCMC) method implemented with the SAS MI procedure; data imputed following subject discontinuation via this process will be censored out of the resulting dataset so that only intermittent missing data is imputed via this method. Second, monotone missing data will be imputed following subject discontinuation using SAS proc MI. For each stage, MI will be performed within treatment group with covariates for baseline NRS score, use of prior anti-itch medication, and presence of select medical conditions. Should convergence issues occur due to small cell size for the one or both of the categorical covariates at either stage, the appropriate covariate(s) will be removed from the model.

Stage 2: Using the resulting complete datasets, the change from baseline with respect to the 11-point NRS will be calculated; patients will be categorized as responder if they have a 3-point (or greater) improvement over baseline. Week 12 values will serve as the primary timepoint. The 20 MI runs will be analyzed independently using a logistic

---

model and the results combined using SAS proc MIANALYZE. Logistic model covariates will include treatment, baseline NRS score, use of prior anti-itch medication, and presence of select medical conditions. As with the MI, should convergence issues occur due to small cell sizes, the appropriate categorical covariate(s) will be dropped as necessary.

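### Sensitivity 2 imputes adverse-event dropouts from all patients' baseline scores rather than their own baseline, so some with a high baseline count as responders by chance, in either arm

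*Protocol*

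**What the plan says.** Section 8.7.1 describes Sensitivity 2 as a pattern-mixture analysis under missing-not-at-random, with the imputation source chosen by reason for withdrawal. The adverse-event rule opens: "For patients who discontinued study drug due to adverse events, NRS scores missing after discontinuation will be imputed". The source is then given as the baseline distribution of all patients' "daily worst itching score assuming a trimmed normal (from 5 to 10"). The rule does not mention the patient's own baseline or treatment arm.

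The endpoint is a within-patient change. In Section 8.7.1, "The baseline score will be defined as the average of the daily 24-hour Worst Itching Intensity NRS scores collected over the Run-in Period", including the Day 1 value before randomization. In Section 14.6, "patients will be categorized as responder if they have a 3-point (or greater) improvement over baseline". Inclusion criterion 10b (Section 6.2.1) puts that run-in mean at 5 or above, and the scale ends at 10.

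Two other sensitivity analyses accompany it. In Sensitivity 1, "Patients who discontinue study drug early will be considered nonresponders". Sensitivity 3 is a tipping-point analysis that shifts imputed scores in the active arm only, by up to 5 points (Section 14.6).

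**The concern.** Using baseline scores for patients who stop because of an adverse event suggests that they are assumed to return to untreated itch. For a change-from-baseline responder endpoint, that would mean a change near zero and no response. An unconditional draw does something else. A patient with baseline 9 who draws 6 or less is counted as a responder, although the draw says nothing about that patient's improvement. Upward draws for low-baseline patients do not offset this, because those patients are nonresponders already. Compared with zero change from own baseline, the rule can only add responders.

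At stake is whether the one sensitivity analysis that separates dropouts by reason does so cleanly. The primary analysis does not use this rule.

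**Working it through.** **The plan's own figures.** The protocol gives no figure for Sensitivity 2. The response rates and arm size used in step 4 come from Section 8.2: 30% placebo, 50% CR845, 175 per arm. The stated 96% power for that case in Table 4 reproduces at 96.3% with the continuity-corrected two-proportion formula.

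**1. Who can be affected.** Let B be the patient's own baseline mean (5 to 10) and Y the imputed value (5 to 10). Response requires B - Y >= 3, that is Y <= B - 3. Since Y is never below 5, B must be at least 8. At exactly 8 the probability is nil for a continuous draw, so in practice B must exceed 8.

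**2. Chance response at a given baseline, one draw.** This is F(B - 3), where F is the distribution function of the normal trimmed to 5-10. The protocol gives no mean or SD, so the ranges below (mean 6.5, 7, 7.5; SD 1.0, 1.5, 2.0, 2.5) are assumptions.

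- B below 8: 0%
- B = 9: F(6) = 6% to 26%
- B = 10: F(7) = 31% to 67%

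**3. Chance response over all adverse-event dropouts.** With B and Y independent from the same trimmed normal, the rate is the integral over B from 8 to 10 of f(B) F(B - 3), where f is the density. It was checked by numerical integration and by simulation. The last column replaces Y by the mean of seven independent daily draws.

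| Assumed mean, SD | One draw | Mean of seven daily draws |
|---|---|---|
| 6.5, 1.0 | 0.7% | 0.13% |
| 7, 1.0 | 1.0% | 0.11% |
| 7, 1.5 | 3.6% | 0.5-0.6% |
| 7.5, 1.0 | 1.2% | 0.04% |
| 6.5, 2.5 | 6.0% | 1.2% |
| 7.5, 2.5 | 6.2% | 0.7% |

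Over the whole grid the range is about 0.7-6.2% for one draw and about 0.04-1.2% for seven. The rule speaks of a daily score and the endpoint is a weekly mean. The text does not say which is drawn, and that choice alone changes the rate several-fold. Setting each dropout to own baseline gives 0%.

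**4. Effect on the treatment difference.** Let d be the proportion stopping for adverse events and r the chance rate. Assume everyone else responds at 50% (CR845) or 30% (placebo). The difference with own-baseline imputation is (1 - dA) x 0.50 - (1 - dP) x 0.30. The rule adds r x (dA - dP). The dropout rates below are assumptions; r = 5%.

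- 5% and 5%: 0.475 - 0.285 = 19.0%; added 0.05 x 0 = 0.
- 10% and 5%: 0.450 - 0.285 = 16.5%; added 0.05 x 0.05 = 0.25 points, giving 16.75%. In patients: 175 x 0.10 x 0.05 = 0.9 on CR845 and 175 x 0.05 x 0.05 = 0.4 on placebo.
- 15% and 5%: 0.425 - 0.285 = 14.0%; added 0.05 x 0.10 = 0.5 points, giving 14.5%.

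**The case against.** The protocol never says that these patients should return to their own baseline. It says that the analysis draws from different populations according to the reason for withdrawal, and the untreated baseline population is one such population. On that view the choice is between two missing-not-at-random assumptions, and nothing in the protocol is contradicted. This stands in part: the intent is an inference. The mismatch between an unconditional draw and a within-patient responder definition does not depend on intent.

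Zero response is also not a known truth for these patients, since Section 8.2 expects about 30% response even on placebo. The rule remains severe. If 10% of CR845 patients dropped out for adverse events and were imputed at the arm's 50% rate, they would contribute 0.10 x 50% = 5 points of response. Here they contribute 0.10 x 5% = 0.5 points, a cut of 90%. Sensitivity 1 has no such chance responders, and Sensitivity 3 is directed against the active arm. All of this stands and keeps the point minor.

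A reader might infer that the artefact falls mostly in the CR845 arm and so favours the drug. The protocol does not support that. The rule is identical in both arms, and no rate of discontinuation for adverse events is given by arm. Section 4.2.2 says of earlier hemodialysis studies that "patients exposed to CR845 reported more adverse events compared with placebo patients", but that concerns events reported, most of them mild or moderate, and not stopping of study drug. An active-arm excess is possible, and step 4 shows its effect, but it is an assumption.

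**Conclusion.** The point holds as a minor defect. The rule does not condition on the baseline against which response is judged, so adverse-event dropouts with a baseline above 8 can become responders by chance in either arm. The share affected rests on the assumed baseline mean and SD and on whether one value or seven daily values are drawn. The net effect on the treatment difference is nil at equal adverse-event dropout, and 0.25-0.5 points under the assumed imbalances with a 5% chance rate. With averaged daily draws it would be smaller still. The primary analysis, Sensitivity 1 and Sensitivity 3 are untouched, and no conclusion on robustness need rest on Sensitivity 2 alone.

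**What to change.** For adverse-event dropouts in Sensitivity 2, impute the missing weekly mean at or around each patient's own baseline mean, bounded 0-10, and state that weekly values are imputed.

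Any added error should have the within-patient variability of a weekly mean, not of a single day. With normal error centred on own baseline, the chance of a fall of 3 points or more is Phi(-3/SD): 0.1% at SD 1.0, but 2.3% at SD 1.5 and 6.7% at SD 2.0. Too large an error would bring the artefact back.

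The cost is about one sentence and a simple program. Section 8.1 gives the SAP primacy for the double-blind analyses, so the change can be made there before unblinding. The downside is a slightly different, possibly less favourable, sensitivity estimate.

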### 8.7.2 Secondary Efficacy Endpoints

The secondary efficacy endpoints are the:

- Proportion of patients achieving  $\geq 4$ -point improvement from baseline with respect to the weekly mean of the daily 24-hour Worst Itching Intensity NRS at Week 12 (Day 79 to 85) of the Double-blind Treatment Period;
- Proportion of patients achieving  $\geq 3$ -point improvement from baseline with respect to the weekly mean of the daily 24-hour Worst Itching Intensity NRS at Week 8 of the Double-blind Treatment Period;
- Proportion of patients achieving  $\geq 3$ -point improvement from baseline with respect to the weekly mean of the daily 24-hour Worst Itching Intensity NRS at Week 4 of the Double-blind Treatment Period;

- 
- Proportion of patients achieving  $\geq 4$ -point improvement from baseline with respect to the weekly mean of the daily 24-hour Worst Itching Intensity NRS at Week 8 of the Double-blind Treatment Period;
  - Proportion of patients achieving  $\geq 4$ -point improvement from baseline with respect to the weekly mean of the daily 24-hour Worst Itching Intensity NRS at Week 4 of the Double-blind Treatment Period;
  - Change from baseline in itch-related quality of life at the end of Week 12 of the Double-blind Treatment Period, as assessed by the Skindex-10 Scale total score;
  - Change from baseline in itch-related quality of life at the end of Week 12 of the Double-blind Treatment Period, as assessed by the 5-D Itch Scale total score.

The proportion of patients achieving  $\geq 4$ -point improvement from baseline at Week 12 of the Double-blind Treatment Period, the proportion of patients achieving  $\geq 3$ -point improvement from baseline at Week 8 and Week 4, and the proportion of patients achieving  $\geq 4$ -point improvement from baseline at Week 8 and Week 4 with respect to the weekly mean of the daily 24-hour Worst Itching Intensity NRS will be analyzed following a methodology similar to the one employed for the primary analysis of the primary endpoint.

The Skindex-10 Scale total score and the 5-D Itch Scale total score change from baseline at Week 12 will be analyzed using an analysis of covariance (ANCOVA) model that will contain treatment as fixed effect, with baseline score, region, and the randomization stratification variables as covariates. The baseline 5-D total score and the Skindex-10 total score will be defined as the value collected on Day 1, prior to randomization.

For each domain in each questionnaire, missing values at Week 12 will be imputed using an MI approach, assuming that patients who discontinue double-blind treatment early would have similar domain scores as other patients in their respective treatment arm that have complete data:

- Intermittent missing scores will first be imputed using the Markov Chain Monte Carlo (MCMC) method implemented with the SAS MI procedure, which is appropriate for non-monotonic missing data;
- The monotone missing values will then be multiply imputed with the SAS MI procedure using the monotone regression method;
- For each stage, MI will be performed within treatment group with covariates for baseline score, region, both randomization stratification factors, and all non-missing visit scores for each domain of the questionnaire;
- For each questionnaire, the total score at each visit will be computed from the domain scores for each imputed dataset;

- 
- The ANCOVA analysis described above will be implemented for each imputed dataset. Results of the ANCOVA on the multiply imputed data sets will be summarized by the SAS MIANALYZE procedure.

The LS means, standard errors, 95% CIs, and differences between treatment groups reported with LS means, standard errors, and 95% CIs derived from the ANCOVA on the imputed datasets will be reported.

Additionally, a sensitivity analysis of the 5D Itch scale and the Skindex-10 scale will be performed to describe the time course of the treatment response over the 12-week treatment period using a mixed effects model with repeated measures (MMRM). The model will contain treatment, week, and treatment-by-week interaction as fixed effects; baseline score, prior anti-itch medication usage, presence of specific medical conditions, and country/region as covariates. Repeated measures will include values collected at the end of Weeks 4, 8, 10, and 12 (end of treatment). It is important to note that, in HD patients, the study drug administered during the last dialysis of a particular week is not cleared until the first dialysis of the next week. Therefore, measurements that would reflect treatment effect at the end of a specific week (eg. Week 4) will actually be collected during the first day of the next week (eg, Week 5).

An unstructured covariance matrix will be used to model the within-subject errors. Should the model fail to converge, a compound symmetric covariance matrix will be used instead. The Kenward-Roger approximation will be used to estimate the denominator degrees of freedom. Missing scores will not be imputed. Assuming that the data are MAR, the estimates of the treatment differences calculated from the MMRM described above are unbiased.

Standard descriptive statistics will be reported for each time point on the values and changes from baseline along with the least squares (LS) means, standard errors, 95% CIs and differences between treatment groups reported with LS means, standard errors, and 95% CIs.

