#### **8.7.4 Additional Efficacy Endpoints**

##### **8.7.4.1 Itch-intensity Measures**

- Proportion of patients who have an improvement from baseline at Week 12 of the Double-blind period with respect to the weekly mean of the 24-hour Worst Itching Intensity NRS scores  $\geq 1$  and  $\geq 2$ . The calculation of the proportions will be based on the NRS data using a multiple imputation (MI) approach for the missing data as in the primary efficacy analysis. A figure presenting the proportion of patients who have an improvement from baseline in NRS scores at Week 12 that is  $\geq 1$ ,  $\geq 2$ ,  $\geq 3$ , and  $\geq 4$  will be prepared.
- Change from baseline in the weekly mean of the 24-hour Worst Itching Intensity NRS score at each week of the Double-blind Treatment Period (Week 1 to

Week 12). Treatment differences between CR845 and placebo at each postbaseline time point will be evaluated using the same MMRM detailed in [Section 8.7.2](#).

- Proportion of patients who rate their itch condition as “Very much improved” or “Much Improved” at the end of Week 12 of the Double-blind Treatment Period/end of double-blind treatment, as measured by the Patient Global Impression of Change. Treatment difference will be tested using the Cochran-Mantel-Haenszel test, adjusting for strata. An exact test, such as the Fisher’s Exact Test, may be used if the observed count in a particular cell is small (ie, <5).

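### If the unstructured MMRM fails to converge, the only fallback is compound symmetry with no robust standard error, which can understate the Week 12 standard error in the additional and sensitivity analyses

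*Protocol*

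**What the plan says.** Section 8.7.2 describes an MMRM with treatment, week and their interaction, plus baseline score, prior anti-itch medication, specific medical conditions and country/region. On the covariance it says "An unstructured covariance matrix will be used to model the within-subject errors", followed by "Should the model fail to converge, a compound symmetric covariance matrix will be used instead". It then adds "The Kenward-Roger approximation will be used to estimate the denominator degrees of freedom" and "Missing scores will not be imputed". No structure between the two is named, and no empirical standard error.

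In Section 8.7.2 this model is a sensitivity analysis for the 5-D Itch Scale and Skindex-10, which have four post-baseline visits. Section 8.7.4.1 extends it to an additional endpoint, "Change from baseline in the weekly mean of the 24-hour Worst Itching Intensity NRS score at each week of the Double-blind Treatment Period", from Week 1 to Week 12. Treatment differences there "will be evaluated using the same MMRM detailed in" Section 8.7.2. The fallback rule therefore also governs a 12-visit analysis.

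**The concern.** An unstructured matrix is the hardest covariance to fit, and its size grows quickly with the number of visits. If the 12-visit fit fails, the rule goes from the most flexible structure to one of the most restrictive. Compound symmetry assumes the same variance at every week and the same correlation at every lag.

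With treatment-by-week terms and complete data, the Week 12 treatment difference is still estimated from the Week 12 data. Its model-based standard error, however, comes from a variance pooled over all weeks. If the variance of change increases over time, the late-week confidence intervals are too narrow and the early-week ones too wide. Kenward-Roger starts from the model-based covariance, so it does not repair this.

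Change in weekly mean NRS was the primary endpoint of the Phase 2 dose-ranging study (Section 4.2.3). This MMRM is thus the analysis most comparable with the earlier evidence, and its standard errors and confidence intervals will be read closely.

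**Working it through.** The protocol states no figure for the MMRM standard errors, so there is none to reproduce. Tables 4 and 5 concern a chi-square test of responder rates and do not bear on this.

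**Size of the covariance model.** An unstructured matrix for T visits has T(T+1)/2 parameters: 4 × 5/2 = 10 for the 5-D and Skindex-10, and 12 × 13/2 = 78 for the weekly NRS.

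**Inputs from the protocol.** There are 175 patients per arm (Section 8.2). Section 4.2.3 gives a Phase 2 standard error of Week 8 NRS change of 0.38 with n = 44 at 0.5 mcg/kg, so SD ≈ 0.38 × √44 = 2.52. All doses together have a standard error of 0.22 with n = 44 + 41 + 44 = 129, so SD ≈ 0.22 × √129 = 2.50. A value of 2.5 is used for Week 12.

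**Assumptions, not in the protocol.** These are the SD at the other weeks, the within-patient correlation and the dropout rate. Each is varied below.

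**Formulas (complete data).**
- True Week 12 SE = SD₁₂ × √(2/175). With SD₁₂ = 2.5 this is 2.5 × 0.1069 = 0.267.
- Compound-symmetry model-based SE = √(mean of the 12 weekly variances) × √(2/175).
- Actual two-sided error at nominal 5% = 2 × [1 − Φ(1.96 × ratio)], where ratio = model-based SE / true SE.

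**Linear rise in SD from 1.5 to 2.5.** The mean weekly variance is 4.098 and its root is 2.024. The model-based SE is 2.024 × 0.1069 = 0.216. The ratio is 2.024/2.5 = 0.81, so the SE is 19% too small. Type I error is 11.2% and 95% CI coverage 88.8%. At Week 1 the same pooling makes the SE too large, by 2.024/1.5 = 1.35.

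**Linear rise in SD from 2.0 to 2.5.** The mean weekly variance is 5.087 and its root is 2.255. The model-based SE is 0.241. The ratio is 2.255/2.5 = 0.90, so the SE is 10% too small. Type I error is 7.7% and coverage 92.3%.

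**Wider range.** With dropout, the best-fitting compound-symmetric parameters were found for each assumed true covariance. Their model-based SE was then compared with the true SE of the resulting estimate. Dropout was 0, 10 or 20% by Week 12, completely at random. Correlation was AR(1) 0.8 or 0.9, or exchangeable 0.6; the plateau case used AR(1) 0.9 only.

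| Assumed truth for weekly NRS change | Ratio at Week 12 | Type I error |
|---|---|---|
| SD rises linearly from 1.25-2.2 to 2.5, dropout 0-20% | 0.73-0.94 | 6.5-15.5% |
| SD rises from 1.25-2.0, flat at 2.5 from Week 4, dropout 0-20% | 0.88-0.97 | 5.8-8.4% |
| Constant SD, AR(1) 0.8-0.9, dropout 10-20% | 0.95-0.98 | 5.5-6.2% |
| Constant SD with no dropout, or exchangeable correlation | 1.00 | 5.0% |
| SD falls from 2.5 to 2.2, dropout 0-20% | 1.02-1.07 | 3.5-4.6% |

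For the four-visit 5-D and Skindex-10 model, a first-visit SD of 0.8-0.9 times the Week 12 SD gives a ratio of 0.89-0.96 (AR(1) 0.8, dropout 0-20%).

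**Effect of a sandwich SE.** In large samples it recovers the true SE of the compound-symmetry estimate: 0.267 with no dropout, and 0.274-0.302 with 10-20% dropout where the SD reaches 2.5.

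**The case against.** The strongest case against acting has five parts.

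- **No confirmatory result is involved.** The primary endpoint and the five responder secondaries use multiple imputation with logistic regression. The gated Skindex-10 and 5-D tests use multiple imputation with ANCOVA. The MMRM serves only sensitivity and additional analyses. This stands and limits the point. A reader might infer that the study's 5% error rate is at risk; the protocol's testing strategy in Section 8.7.3 does not support that.
- **The trigger may never occur.** With 350 patients and up to 12 values each (about 4,200 observations), the unstructured model may well converge. No failure rate has been estimated. This also stands; 78 parameters make failure more plausible than in the four-visit model, and no more than that.
- **The direction of the error is assumed.** A reader might infer that compound symmetry necessarily gives standard errors that are too small. The protocol reports NRS variability at one Phase 2 time point, which says nothing about a trend. No effect and the opposite effect are both possible, as the table shows.
- **The SAP may say more.** Section 8.1 gives the SAP primacy, and it is not shown. Kenward-Roger is named for the degrees of freedom, and purely model-based errors are inferred from the absence of any alternative. That is fair, but the protocol has itself fixed a specific fallback, and that stated rule can be judged.
- **A named fallback already removes analyst discretion.** True, but an ordered list does so equally well.

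A reader might also take the list of Weeks 4, 8, 10 and 12 in Section 8.7.2 to contradict the weekly NRS analysis. It does not. That list belongs to the 5-D and Skindex-10 and matches their collection schedule, while Section 8.7.4.1 itself states Week 1 to Week 12 for the NRS.

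**Conclusion.** The point holds in conditional form. The protocol fixes a fallback that can understate the Week 12 standard error, and Section 8.7.4.1 carries it to the 12-visit NRS model, where it is most likely to be needed. The 10-19% understatement and 8-11% type I error rest on an assumed linear rise in SD from 1.5-2.0 to 2.5. With constant SD, decaying correlation and 10-20% dropout, the error is smaller (5.5-6.2%). Constant SD with no dropout gives none, and falling SD makes the test conservative.

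The consequence is confined to additional and sensitivity analyses, and only on non-convergence. It is worth correcting because a better rule costs almost nothing, not because the trial's main conclusions depend on it.

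**What to change.** In Section 8.7.2, and in the SAP if it repeats the rule, replace the single fallback with a prespecified order, taking the first structure that converges: unstructured, heterogeneous Toeplitz, heterogeneous AR(1), Toeplitz, and compound symmetry last. State that any structure other than unstructured is reported with empirical (sandwich) standard errors. Fix the order before unblinding.

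The cost is a few lines of text and code. Kenward-Roger is given up in the fallback only, which matters little at 175 per arm. Sandwich errors correct the standard error but not any bias in the estimate from a wrong covariance when dropout is missing at random. The richer structures should therefore be tried first, rather than keeping compound symmetry and adding a sandwich estimator.
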